7.4.4 AF Freedom

A subject will be considered **AF free** for a time period if the subject:

- Does not exhibit AF
- Has sufficient efficacy assessments to determine that AF was not present
- Does not meet failure criteria (including the use of new Class I/III AADs or increased dose of a previously failed Class I/III AAD). Criteria for treatment failure is provided in the study protocol section 1.5.

If a subject exhibits AF or meets failure criteria, the subject will be classified as **not AF free** for that time period. If a subject has insufficient efficacy assessments and does not meet failure criteria, and does not exhibit AF on any efficacy assessments during that period, the subject will be classified as **indeterminate**, and subject to imputation as described in Sections 7.2 and 9.3.

Does not exhibit AF is defined as:

Subject has no atrial fibrillation, where atrial fibrillation is defined as a Holter monitor finding or ECG rhythm of 'AF' or 'Other' with description including atrial fibrillation, where the Holter monitor date or ECG date falls within that period. (Note that findings of AF/AFL/AT without specific information that AF is present will not be considered demonstration of AF).

A list of descriptions for 'Other' results from the Holter monitor and ECG will be tabulated and provided to the Medical Monitor or designee to determine whether the description is indicative of the subject having AF. This tabulation will not include subject identifiers or treatment arm. Additional information collected on the Holter monitor, ECG, or Rhythm Disturbance Evaluation eCRF from that visit may also be provided to help with classification. This information will be finalized prior to database lock and subsequent unblinding of study sponsor, and incorporated into analysis datasets in order to determine if subjects meet criteria for to be AF free at a given assessment, and hence determine if the subject is AF free for a given period of time.

Has sufficient efficacy assessments to determine that AF was not present is defined as:

A subject must have either Holter monitor, ECG, or Rhythm Disturbance Evaluation results indicating no AF at each scheduled visit within that period (for example, both 6 & 12 month visits, for the period after the blanking period through the 12 month visit), in order to be considered AF free for that period.

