2.1.3 Secondary Objectives

The secondary objectives are to demonstrate the efficacy of EPi-Sense-AF as:

- A 90% reduction in the subject's baseline AF burden (percent of time a subject is in AF) at 12 months post-procedure in the presence or absence of Class I/III AADs.
- Change in QoL measures from baseline to 12 months post-procedure.
- Change in six minute walk test scores from baseline to 12 months post-procedure.

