7.2 Imputation of AF/ AFL/AT Freedom

Subjects who were randomized and received study procedure but have no post-treatment assessments will be conservatively imputed as having failed to achieve freedom from AF/ AFL/AT (e.g., treatment failure). Similarly, subjects who were randomized and received study procedure but do not have treatment assessments following the 3-month blanking period (as described in Section 7.4.2), or a visit was performed but insufficient information was collected to determine whether or not AF/AFL/AT was experienced and/or whether Class I/III AADs were administered, will also be imputed as treatment failures. Subjects who do not have complete information for the efficacy evaluation period (for example, withdrew before 12 months) but have sufficient information to conclude that they would be classified as *not* AF/AFL/AT free (such as: new or increased dose of Class I/III AAD or documented findings of AF/AFL/AT) will be considered treatment failures. These subjects will *not* be considered to have been imputed, for the purpose of tipping point or multiple imputation analyses, as it is clear that they would have been treatment failures even if complete information had been collected.

The same approach will be utilized to impute AF freedom for secondary efficacy analyses.

A tipping-point analysis will also be performed, as described in Section 9.3.2, which will be performed on un-imputed data. Further details on criteria for treatment failure are provided in study protocol Section 1.5.

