If a subject exhibits AF, AFL, or AT or meets failure criteria, the subject will be classified as **not AF/AFL/AT free** for that time period. If a subject has insufficient efficacy assessments and does not meet failure criteria, and does not exhibit AF/AFL/AT on any efficacy assessments during that period, the subject will be classified as **indeterminate**, and subject to imputation as described in Sections 7.2 and 9.3. Further details on criteria for treatment failure are provided in study protocol section 1.5.

Does not exhibit AF, AFL, or AT is defined as:

- Has no atrial fibrillation, where atrial fibrillation is defined as a Holter monitor finding or ECG rhythm of 'AF' or 'Other' with description including atrial

fibrillation, where the Holter monitor date or ECG date falls within that period.

- Has no atrial flutter, where atrial flutter is defined as a Holter monitor finding or ECG rhythm of 'Typical AFL (Right Atrial)' or 'Atypical AFL (Left Atrial)' or 'Other' with description including atrial flutter, where the Holter monitor date or ECG date falls within that period.
- Has no atrial tachycardia, where atrial tachycardia is defined as a Holter monitor finding or ECG rhythm of 'AT' or 'Other' with description including atrial tachycardia, where the Holter monitor date or ECG date falls within that period.
- Has a Rhythm Disturbance Evaluation eCRF where 'any symptomatic AF/AFL/AT episodes' is marked No or Unknown at each visit where completed.
- Has a Holter monitor eCRF where the number of >30 second AF/AFL/AT episodes is 0 for each eCRF page where the Holter monitor date falls within that period.

A list of descriptions for 'Other' results from the Holter monitor and ECG will be tabulated and provided to the Medical Monitor or designee to determine whether the description is indicative of the subject having AF/AFL/AT. This tabulation will not include subject identifiers or treatment arm. Additional information collected on the Holter monitor, ECG, or Rhythm Disturbance Evaluation eCRF from that visit may also be provided to help with classification. This information will be finalized prior to database lock and subsequent unblinding of study sponsor, and incorporated into analysis datasets in order to determine if subjects meet criteria for to be AF/AFL/AT free at a given assessment, and hence determine if the subject is AF/AFL/AT free for a given period of time.

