9.4 Secondary Efficacy Analysis

All secondary analyses will be performed on the ITT population. These analyses may be repeated on the mITT and PP populations.

9.4.1 $\geq 90\%$ Reduction in AF Burden

The AF burden, as a percentage, is recorded on the Holter Monitor eCRF. The recorded values and percent change from baseline in AF burden will be summarized by time point at 6, 12, and 18 months post-procedure.

The percent change from baseline at 12 months will be categorized as $\geq 90\%$ reduction (percent change $\leq -90\%$) or $< 90\%$ reduction (percent change $> -90\%$). The proportion of subjects achieving $\geq 90\%$ reduction at 12 months will be compared between treatment arms using Fisher's Exact test.

This analysis will be repeated for the following subsets of subjects:

- Subjects who have taken a Class I/III AAD during the efficacy evaluation period (excluding previously failed Class I/III AADs with no increase in dosage).

- Subjects who have *not* taken a Class I/III AAD during the efficacy evaluation period (excluding previously failed Class I/III AADs with no increase in dosage).
- Subjects who have taken any Class I/III AAD during the efficacy evaluation period.

No imputation will be performed for missing data.

These analysis (on all subjects and the three subsets) will also be repeated where subjects with a new or increased dosage of Class I/III AADs during the efficacy evaluation period will be categorized as not having achieved $\geq 90\%$ reduction. This will be performed on the ITT population. No imputation will be performed for missing data.

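### SAP 7.4.4 does not say how to score AF freedom when the Holter form records AF burden but its finding is not labelled AF

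*SAP*

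**What the plan says.** SAP 7.4.4 defines AF freedom, which is tested second and fourth in the fixed sequence of SAP 9.2 (test 4 disregards antiarrhythmic drug use). Under it, "atrial fibrillation is defined as a Holter monitor finding or ECG rhythm of 'AF' or 'Other' with description including atrial fibrillation". A note follows: "Note that findings of AF/AFL/AT without specific information that AF is present will not be considered demonstration of AF".

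A sufficiency rule applies as well: "A subject must have either Holter monitor, ECG, or Rhythm Disturbance Evaluation results indicating no AF at each scheduled visit within that period". A subject who fails that rule, shows no AF and meets no failure criterion is indeterminate and passes to SAP 7.2. There, a visit at which "insufficient information was collected to determine whether or not AF/AFL/AT was experienced" leads to imputation as a failure.

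For failure criteria, SAP 7.4.4 refers to Protocol 1.5. Protocol 1.5.1 makes any Holter episode of AF, AFL or AT lasting 30 seconds or longer a failure. The list that SAP 7.4.4 then sets out covers drug use, cardioversion and left-sided ablation, and has no Holter episode item.

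The Holter form carries two further fields. SAP 9.4.1 says: "The AF burden, as a percentage, is recorded on the Holter Monitor eCRF". SAP 2.1.3 defines that burden as the share of time spent in AF, and tests 1 and 3 are built on it. SAP 7.4.5, which defines the primary endpoint, adds a condition on the pooled episode count: "Has a Holter monitor eCRF where the number of >30 second AF/AFL/AT episodes is 0".

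**The concern.** The definition behind tests 2 and 4 rests on one label, while an AF-specific quantity on the same form goes unused. If the two disagree, a subject with recorded time in AF can be reported as free of AF. The primary endpoint does not rely on the label alone, because SAP 7.4.5 adds the episode count. SAP 7.4.4 has no equivalent second check.

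Two things are at stake. The first is consistency: one Holter page could supply AF burden to tests 1 and 3 and support AF freedom in tests 2 and 4. The second is reproducibility. The section cites Protocol 1.5 but lists a shorter set of criteria, so two programmers could score the same subject differently. Test 2 stands early in a 19-step sequence that stops at the first non-significant result, so its definition should leave no choice open.

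**Working it through.** **Step 1. Which Holter fields each endpoint uses.**

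| Holter field | Specific to AF? | Primary (SAP 7.4.5) | Tests 2 and 4 (SAP 7.4.4) | Tests 1 and 3 (SAP 9.4.1) |
|---|---|---|---|---|
| Finding label | Yes, if labelled AF | Used | Used | Not used |
| Count of episodes over 30 s | No, pools AF, AFL and AT | Used, must be 0 | Not used | Not used |
| AF burden (%) | Yes | Not used | Not used | Used |

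**Step 2. One hypothetical record.** The 12-month Holter has AF burden 4%, pooled count 2, and a finding that is neither AF nor Other described as AF. The 12-month ECG shows no AF, the 6-month assessments are clean, and there is no new or increased drug, cardioversion or ablation.

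- Primary endpoint: failure, because the count is 2 and not 0.
- Tests 1 and 3: the 4% enters the analysis. With baseline burden B, percent change is 100 × (4 − B)/B, which is −90% or lower when B ≥ 4/0.10 = 40%. The subject may pass or fail these tests, but AF is on record either way.
- Tests 2 and 4, from the criteria listed in SAP 7.4.4: no AF label, the ECG satisfies the sufficiency rule, and no listed failure is met. The subject is AF free.
- Same record without an ECG or Rhythm Disturbance Evaluation showing no AF: indeterminate, then failure under SAP 7.2, unless the Holter itself is taken as showing no AF.
- Same record read through the citation of Protocol 1.5: failure, because there are two episodes over 30 seconds.

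The last reading does not settle the matter either. The Protocol criterion pools AF with AFL and AT. Applied unchanged, it would make AFL or AT a failure of an AF-only endpoint, against the note and against the exemption of right-sided flutter ablation in SAP 7.4.4.

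**Step 3. Size.** The plan states no figure for AF freedom. Its only sample-size figure, 153, is for the primary endpoint (SAP 4: 40% v 65%, two-sided 0.05, 80% power, 2:1, 10% dropout). With pooled p = (0.40 + 2 × 0.65)/3 = 0.567:

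n(control) = [1.96 √(1.5 × 0.567 × 0.433) + 0.842 √(0.40 × 0.60 + 0.65 × 0.35/2)]² / 0.25² = 45.7, so 46.

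The total is 3 × 46 = 138, and 138/0.9 = 153.3, which matches the stated 153 to rounding.

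The following is illustration only. Suppose a share m of true AF failures is scored AF free in both arms. The observed rate is p + m(1 − p), and the difference is 0.25(1 − m). The 40% and 65% are borrowed from the primary endpoint, and m has no source in the documents.

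| m | Control | Treatment | Difference (points) | Power, 46:92 | Power, 51:102 |
|---|---|---|---|---|---|
| 0 | 40% | 65% | 25 | 80.3% | 84.2% |
| 5% | 43% | 66.75% | 23.75 | 76.4% | 80.6% |
| 10% | 46% | 68.5% | 22.5 | 72.4% | 76.7% |
| 20% | 52% | 72% | 20 | 64.1% | 68.5% |

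The direction depends on m being equal across arms. If true rates were 50% in both arms at 51:102 and the miss occurred only in the treatment arm, the treatment rate would be 0.5 + 0.5m. The chance of a false win would then rise from 2.5% to 4.8%, 8.5% and 21.7% for m = 5%, 10% and 20%.

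**The case against.** The strongest reply is that the gap needs a form that conflicts with itself. AF entered in the finding field already makes the subject not AF free, and a non-zero burden implies that the reader identified AF. Protocol 1.5.1 and 6.0 send Holters to an independent reviewer, and Protocol 6.8 provides for data checks and queries. The Holter form is not in the documents, so whether it permits the conflict is unknown. This stands as a limit on frequency. It does not remove the gap, because no stated check compares label with burden, and SAP 7.4.4 gives no rule if they differ.

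A reader might infer that SAP 7.4.4 turns insufficient information into success, against SAP 7.2. The text does not go that far. The note says that an untyped finding does not demonstrate AF. The subject still needs a result showing no AF at each visit, and otherwise becomes indeterminate and is imputed as a failure. What remains is that one clean ECG, which is scheduled at both 6 and 12 months, can satisfy the rule.

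A reader might also infer that the pooled count should simply be added and the note deleted. The documents do not support this. The count mixes AF, AFL and AT, and the note keeps the endpoint specific to AF. Even pairing burden with the count can mislead: a few seconds of AF plus one AT episode over 30 seconds would be scored as AF.

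The Medical Monitor review does not close the gap as written. It covers only descriptions entered under Other, and supplying further form data is optional.

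**Conclusion.** The point holds in a limited form. SAP 7.4.4 leaves a Holter with AF burden above 0 and no AF label without an explicit rule. Its listed criteria can score such a subject AF free when another assessment at the visit shows no AF. It also cites Protocol 1.5 for failure criteria and then omits the Holter episode criterion found there. Burden is specific information about AF, so the note does not justify leaving it out.

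The reach is tests 2 and 4. The primary endpoint is protected by the episode count in SAP 7.4.5. The number of subjects affected cannot be determined from the documents.

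A reader might infer from the illustration that tests 2 and 4 are underpowered or biased in a known direction. That is not established. The rates belong to the primary endpoint and the share missed is assumed. Some of those subjects would also fail by ECG, drug use, cardioversion or ablation, and the direction reverses if the miss falls on the treatment arm alone. No figure stated in the plan changes.

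**What to change.** Amend SAP 7.4.4 before database lock and unblinding:

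1. State that a Holter in the period with AF burden above 0 is specific information that AF is present, and counts as exhibiting AF when it represents an AF episode of the Protocol 1.5 duration.
2. Where the form does not show whether the qualifying episode was AF (a positive pooled count with no AF, AFL or AT label), send the record to the treatment-blinded Medical Monitor review already planned for Other findings. If it stays untyped, treat it as indeterminate under SAP 7.2.
3. Keep the note for findings typed as AFL or AT, so that the endpoint stays specific to AF.
4. Reconcile the failure list in SAP 7.4.4 with Protocol 1.5, saying which Protocol criteria apply to AF freedom and in what form.

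The cost is SAP wording and a modest addition to a review that is already planned. According to the SAP, both fields are on the Holter form. Reported AF freedom may be slightly lower in both arms.

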If a subject exhibits AF, AFL, or AT or meets failure criteria, the subject will be classified as **not AF/AFL/AT free** for that time period. If a subject has insufficient efficacy assessments and does not meet failure criteria, and does not exhibit AF/AFL/AT on any efficacy assessments during that period, the subject will be classified as **indeterminate**, and subject to imputation as described in Sections 7.2 and 9.3. Further details on criteria for treatment failure are provided in study protocol section 1.5.

Does not exhibit AF, AFL, or AT is defined as:

- Has no atrial fibrillation, where atrial fibrillation is defined as a Holter monitor finding or ECG rhythm of 'AF' or 'Other' with description including atrial

fibrillation, where the Holter monitor date or ECG date falls within that period.

- Has no atrial flutter, where atrial flutter is defined as a Holter monitor finding or ECG rhythm of 'Typical AFL (Right Atrial)' or 'Atypical AFL (Left Atrial)' or 'Other' with description including atrial flutter, where the Holter monitor date or ECG date falls within that period.
- Has no atrial tachycardia, where atrial tachycardia is defined as a Holter monitor finding or ECG rhythm of 'AT' or 'Other' with description including atrial tachycardia, where the Holter monitor date or ECG date falls within that period.
- Has a Rhythm Disturbance Evaluation eCRF where 'any symptomatic AF/AFL/AT episodes' is marked No or Unknown at each visit where completed.
- Has a Holter monitor eCRF where the number of >30 second AF/AFL/AT episodes is 0 for each eCRF page where the Holter monitor date falls within that period.

A list of descriptions for 'Other' results from the Holter monitor and ECG will be tabulated and provided to the Medical Monitor or designee to determine whether the description is indicative of the subject having AF/AFL/AT. This tabulation will not include subject identifiers or treatment arm. Additional information collected on the Holter monitor, ECG, or Rhythm Disturbance Evaluation eCRF from that visit may also be provided to help with classification. This information will be finalized prior to database lock and subsequent unblinding of study sponsor, and incorporated into analysis datasets in order to determine if subjects meet criteria for to be AF/AFL/AT free at a given assessment, and hence determine if the subject is AF/AFL/AT free for a given period of time.

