#### **1.5 Study Endpoints**

##### **1.5.1 Primary Efficacy Endpoints**

The primary efficacy endpoint is success or failure to be AF/AT/AFL free absent class I and III AADs except for a previously failed or intolerant class I or III AAD with no increase in dosage following the 3 month blanking period through the 12 months post procedure follow-up visit.

The results of the holter data used for the primary efficacy endpoint evaluation will be evaluated by an independent reviewer thus maintaining the objectivity of the primary efficacy endpoint.

Subjects will be considered primary efficacy failures if any of the following conditions are observed:

- Any electrocardiographically documented AF/AFL/AT episode of 30 sec duration or longer by Holter, event monitor or rhythm strip; or for the full 10 second recording of a standard 12 lead ECG following the 3 month blanking period through the 12 months post procedure follow-up visit.
- The use of a new or an increase in the dose of a previously failed class I or class III AAD following the 3 month blanking period through the 12 months post procedure follow-up visit.
- DC cardioversion for AF/AFL/AT following the 3 month blanking period through the 12 months post procedure follow-up visit.
- Subsequent left-sided catheter ablation for AF/AFL/AT at anytime during the 12 months post procedure follow-up visit.
- Catheter ablation for right-sided typical atrial flutter following the 3 month blanking period through the 12 months post procedure follow-up visit.

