2.3 Study Endpoints

2.3.1 Primary Efficacy Endpoints

The primary efficacy endpoint is success or failure to be AF/AT/AFL free absent class I and III AADs except for a previously failed or intolerant class I or III AAD with no increase in dosage following the 3 month blanking period through the 12 months post procedure follow-up visit.

Subjects will be considered primary efficacy failures if any of the following conditions are observed:

- Any electrocardiographically documented AF/AFL/AT episode of 30 sec duration or longer by Holter, event monitor or rhythm strip; or for the full 10 second recording of a standard 12 lead ECG following the 3 month blanking period through the 12 months post procedure follow-up visit.
- The use of a new or an increase in the dose of a previously failed class I or class III AAD following the 3 month blanking period through the 12 months post procedure follow-up visit.
- DC cardioversion for AF/AFL/AT following the 3 month blanking period through the 12 months post procedure follow-up visit.
- Subsequent left-sided catheter ablation for AF/AFL/AT at anytime during the 12 months post procedure follow-up visit.
- Catheter ablation for right-sided typical atrial flutter following the 3 month blanking period through the 12 months post procedure follow-up visit.

As described in Section 7.4.2, the blanking period is the period from index procedure through 3 months post-procedure visit.

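### SAP 7.4.5 does not derive the primary endpoint stated in Protocol 1.5.1 and SAP 2.3.1: its rhythm labels carry no duration test, and its symptom box needs no recording

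*SAP*

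**What the plan says.** SAP 2.3.1 lists as a primary failure "Any electrocardiographically documented AF/AFL/AT episode of 30 sec duration or longer by Holter, event monitor or rhythm strip". A second test covers the 12-lead ECG. Protocol 1.5.1 states the same two tests and words the second as "or for the full 10 second recording of a standard 12 lead ECG".

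SAP 7.4.5 turns this into data rules. A subject does not exhibit AF, AFL or AT only if five conditions all hold:

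1. AF: "Has no atrial fibrillation, where atrial fibrillation is defined as a Holter monitor finding or ECG rhythm of 'AF" (or Other with a matching description).
2. AFL: "Has no atrial flutter, where atrial flutter is defined as a Holter monitor finding or ECG rhythm of 'Typical AFL (Right Atrial" (or the atypical form, or Other with a matching description).
3. AT: "Has no atrial tachycardia, where atrial tachycardia is defined as a Holter monitor finding or ECG rhythm of 'AT" (or Other with a matching description).
4. The symptomatic-episode question on the Rhythm Disturbance Evaluation eCRF is answered No or Unknown wherever it was completed.
5. "Has a Holter monitor eCRF where the number of >30 second AF/AFL/AT episodes is 0", for each Holter page dated in the period.

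A subject who exhibits any of the three rhythms is classed as not free. SAP 9.1 cites both 2.3.1 and 7.4.5 as the detail of the primary endpoint and gives neither precedence. SAP 13 lists departures from the protocol, including the extension of cardioversion to the pharmacologic kind, but nothing about rhythm duration or recording source.

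**The concern.** The endpoint turns on duration and on an electrocardiographic record. The derivation turns on a label or a tick box, with a duration test on one source standing beside them. Two programmers, one following 2.3.1 and the other 7.4.5, could classify the same subject differently on the primary endpoint of a pivotal open-label trial. Independent review is specified for the Holters, but not for the ECG labels or the symptom box. The duration rule is therefore a large part of what keeps the endpoint objective, and it is the part that the derivation loosens. The mismatch can also work the other way, by letting a documented qualifying episode go uncounted.

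**Working it through.** **Step 1. Apply both rules to the same record.** Each row assumes that nothing else in the period triggers failure.

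| Record in the evaluation period | SAP 2.3.1 | SAP 7.4.5 as written |
|---|---|---|
| Holter labelled AT, every run under 30 s, episode count 0 | not a failure | failure (condition 3) |
| Holter episode of exactly 30 s | failure | not caught by condition 5, which needs more than 30 s; depends on the label |
| Event-monitor or strip episode of 30 s or longer, not marked symptomatic | failure | no condition reads it |
| The same episode, marked symptomatic | failure | failure (condition 4) |
| Symptom box Yes, no recording | not a failure | failure (condition 4) |
| 12-lead ECG labelled AF, present for part of the 10 s | not a failure | failure, unless the label means the whole recording |

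The rules agree in one row of six. Rows 1 and 5 make 7.4.5 stricter than the endpoint; row 3 makes it more lenient.

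**Step 2. Reproduce the planned sample size.** Inputs from SAP 4: 40% and 65% success, two-sided alpha 0.05, power 80%, 2:1 allocation, 10% dropout, 102:51. With pooled p = (0.40 + 2 × 0.65)/3 = 0.5667, the control arm needs

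n = [1.96 √(1.5 × 0.5667 × 0.4333) + 0.8416 √(0.40 × 0.60 + 0.65 × 0.35/2)]² / 0.25² = 45.7, so 46, with 92 in the treatment arm.

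Adding 10% gives 46 × 1.10 = 50.6, so 51, hence 51 + 102 = 153. The plan's figure reproduces and is not in dispute.

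**Step 3. Power at the stated rates after 10% loss.** The arms are 51 × 0.9 = 45.9 and 102 × 0.9 = 91.8. Power = Φ[(d − 1.96 se0)/se1], where d is the difference, se0 the standard error under the pooled rate and se1 that under the separate rates. Here se0 = 0.0896 and se1 = 0.0878, so power = Φ[(0.25 − 0.1756)/0.0878] = 80.2%.

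**Step 4. Illustration.** The documents give no rate for either error. Assume a share m of true successes in each arm is failed on a label alone, so each success rate becomes p(1 − m):

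| m (assumed) | Control | Treatment | Difference | Power after 10% loss |
|---|---|---|---|---|
| 0 | 40.0% | 65.0% | 25.00 points | 80.2% |
| 5% | 38.0% | 61.75% | 23.75 points | 75.6% |
| 10% | 36.0% | 58.5% | 22.50 points | 70.8% |
| 20% | 32.0% | 52.0% | 20.00 points | 60.8% |

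Now assume instead that a share u of true failures in each arm is missed because it appears only on an event monitor or strip, so each rate becomes p + u(1 − p). At u = 5% the rates are 43.0% and 66.75%, with power 76.3%. At u = 20% they are 52% and 72%, with power 64.0%. The two errors move the success rates in opposite directions, but each narrows the difference when it is equal in both arms.

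**The case against.** Several stronger readings are tempting, and the documents do not support them.

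- *That 7.4.5 has no 30-second test.* It has one for Holter, in the fifth condition. The fault is that this condition does not qualify the labels.
- *That event-monitor and strip episodes have no route at all.* Symptomatic ones can enter through the fourth condition. SAP 2.3.1 names both sources, and 7.4.5 refers to Protocol 1.5 for further failure criteria. Neither source is in the visit schedule, and the only between-visit prompt (Protocol 6.4) concerns symptomatic episodes. Untreated episodes that are asymptomatic or not entered in the box remain uncovered.
- *That free text fails a subject automatically.* Other descriptions go to the Medical Monitor or designee without subject identifiers or treatment arm. That is a judgement step, although it asks which rhythm was present, not how long it lasted.
- *That ECG labels certainly capture partial recordings.* An ECG rhythm may well mean the rhythm of the whole 10 seconds. The SAP should say so.
- *That SAP 7.4.4 contradicts its own endpoint.* It uses the same kind of label ("atrial fibrillation is defined as a Holter monitor finding or ECG rhythm of 'AF"), but the secondary AF-free endpoints state no 30-second threshold. This is an open question, not a contradiction.
- *That a known amount of power is lost, or that the device is favoured.* The shares are assumed. SAP 1 sends the reader to the eCRFs for data collection details, and these are not in the documents. The independent Holter reader may enter a label only for qualifying episodes. If the arms were affected equally, the label rule would cost power without favouring the device.

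The cumulative structure of the five conditions survives all of this, as do the unsupported symptom box and the absence of any declaration in SAP 13.

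**Conclusion.** The point holds as a conflict between two written definitions of the primary endpoint. By its text, SAP 7.4.5 fails a subject on a Holter label without a duration test and on a symptom answer without a recording. It uses more than 30 seconds where the endpoint includes 30, and it does not explicitly capture a qualifying monitor or strip episode that is not marked symptomatic. How many subjects this would reclassify cannot be known from the documents. The fall in power from about 80% to between 76% and 61% rests on an assumed 5% to 20% share of true successes, equal in both arms, and is not an estimate. The net direction for the observed success rates is open. The case for acting is that the primary endpoint should have one definition before lock and that giving it one is cheap.

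**What to change.** Before database lock, amend SAP 7.4.5 as follows.

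- Count a Holter label as failure only when the independent reviewer's record shows at least one AF/AFL/AT episode of 30 seconds or longer. Change the count from more than 30 seconds to 30 or longer.
- Where a label is present but the count or duration is missing, have the independent reviewer, not the open-label site, resolve it blinded to arm. If it stays unresolved, the subject remains a failure.
- State that an ECG label means the arrhythmia was present for the full 10-second 12-lead recording.
- Count any dated event-monitor or rhythm-strip episode of 30 seconds or longer in the evaluation period as failure, symptomatic or not. Require such a recording behind a Yes in the symptom box.
- In 7.4.4, state whether the same threshold applies to AF freedom.

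If the broader label rule is intended, declare it in SAP 2.3.1 and SAP 13 instead.

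The cost is minor programming and a limited number of reader queries. Observed success rates may move slightly in either direction.
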